9.3 POPULATIONS FOR ANALYSES

For purposes of analysis, the following populations are defined in [Table 3](#).

Table 3 - Populations for analyses

Population	Description
Enrolled	All participants who sign the ICF.
Randomized	The randomized population includes all patients with a treatment kit number allocated and recorded in the IRT database, and regardless of whether the treatment kit was used or not. Patients treated without being randomized will not be considered randomized and will not be included in any efficacy population, but will be included in the safety population.
Intent-to-treat (ITT)	All randomized patients, and will be analyzed according to the treatment group allocated by randomization
Efficacy	The ITT Population
Safety	The safety population includes all patients who actually received at least 1 dose or partial dose of the IMP, analyzed according to the treatment actually received. Randomized patients for whom it is unclear whether the study medication was taken will be included in the safety population as randomized.

Abbreviations: ICF = informed consent form; IRT = interactive response technology; ITT = intent-to-treat

9.4 STATISTICAL ANALYSES

The statistical analysis plan will be developed and finalized before database lock. This section is a summary of the planned statistical analyses of the primary and secondary endpoints.

9.4.1 Efficacy analyses

Note: All daily assessments (eg, sleep NRS, actigraphy parameters, sleep diary, etc.) will be analyzed as weekly averages for the week immediately preceding the study visit. Thus, the baseline value will correspond to the assessments completed during the week preceding randomization.

Table 4 - Efficacy analyses

Endpoint	Statistical Analysis Methods
Primary Percent change from baseline to week 12 in sleep NRS	Percent change from baseline will be analyzed using a mixed effect model with repeated measures (MMRM) with treatment, baseline value, randomization stratum, week, treatment by week interaction, and baseline value by week interaction terms (all as fixed effects) in the model. An unstructured correlation matrix will be used to model the within-patient errors. No imputations for missing values will be carried out for the primary analysis. LS mean changes between the dupilumab group and placebo, the corresponding 95% CI of the differences and p-values will be provided.

Secondary

Change from baseline to week 12 in sleep efficiency, total sleep time, wake after sleep onset, sleep onset latency based on actigraph data

The similar approach as for the analysis of primary endpoint will be used.

A similar approach as for the analysis of primary endpoint will be used.

Percent change from baseline to week 12 in Pruritus NRS

A similar approach as for the analysis of primary endpoint will be used.

Change from baseline to week 12 in SCORing Atopic Dermatitis (SCORAD) total score

A similar approach as for the analysis of primary endpoint will be used.

Change from baseline to week 12 in SCORAD sleep VAS

A similar approach as for the analysis of primary endpoint will be used.

Change from baseline to week 12 in Dermatology Quality Life Index (DLQI)

A similar approach as for the analysis of primary endpoint will be used.

Change from baseline to week 12 in Patient Oriented Eczema Measure (POEM) total score

A similar approach as for the analysis of primary endpoint will be used.

Change from baseline to week 12 in PROMIS Sleep Related Impairment SF8a total score

Proportion of patients with EASI50, EASI75 (reduction of EASI score by $\geq 50\%$ and $\geq 75\%$ from baseline, respectively) at each time point

will be analyzed via the Cochran-mantel-Haenszel test adjusted by the randomization stratum at each time point

Exploratory

Will be described in the statistical analysis plan finalized before database lock prior to the week 12 interim analysis. Of note, formal statistical comparisons will not be performed on the PSG endpoints due to the limited sample size of the sub-study; the analyses will be limited to providing summary statistics for the specified endpoints.

9.4.2 Safety analyses

All safety analyses will be performed on the Safety Population.

Table 5 - Safety analyses

Endpoint	Statistical Analysis Methods
AE, SAE, AE leading to death, AE leading to permanent treatment discontinuation	Treatment emergent adverse event (TEAE) incidence tables will be presented by system organ class (SOC), high-level group term (HLGT), high-level term (HLT) and preferred term (PT) for each treatment group and overall, showing the number (n) and percentage (%) of patients experiencing a TEAE. Multiple occurrences of the same event in the same patient will be counted only once in the tables. The denominator for computation of percentages is the safety population within each treatment group. In addition, TEAEs will be described according to maximum intensity and relation to the study drug. AEs that occur outside the treatment emergent period will be summarized separately. Proportion of patients with at least 1 TEAE, treatment emergent SAE, TEAE leading to death, and TEAE leading to permanent treatment discontinuation will be tabulated by treatment group and overall. All Tables will be provided separately for the double-blind treatment period, and for the entire study.

9.4.3 Other analyses

Not applicable.

9.5 INTERIM ANALYSES

After all patients have completed the 12 weeks of double-blind, randomized treatment period, the database for this portion of the study will be locked, and the study will be unblinded; Comparative efficacy data will be analyzed following this database lock.

Since the unblinding will be performed after the randomized treatment period, no adjustments to the type I error is needed.

Once all patients complete the 24 weeks post randomization, the final database lock will be performed, and the remaining data will be analyzed.

9.6 DATA MONITORING COMMITTEE (DMC)

No DMC is planned for this study.

10 SUPPORTING DOCUMENTATION AND OPERATIONAL CONSIDERATIONS

10.1 APPENDIX 1: REGULATORY, ETHICAL, AND STUDY OVERSIGHT CONSIDERATIONS

10.1.1 Regulatory and Ethical Considerations

- This study will be conducted in accordance with the protocol and with the following:
 - Consensus ethical principles derived from international guidelines including the Declaration of Helsinki and the applicable amendments and Council for International Organizations of Medical Sciences (CIOMS) International Ethical Guidelines.
 - Applicable ICH Good Clinical Practice (GCP) Guidelines.
 - Applicable laws and regulations.
- The protocol, protocol amendments, ICF, Investigator Brochure, and other relevant documents (eg, advertisements) must be submitted to an IRB/IEC by the Investigator and reviewed and approved by the IRB/IEC before the study is initiated.
- Any amendments to the protocol will require IRB/IEC approval before implementation of changes made to the study design, except for changes necessary to eliminate an immediate hazard to study participants.
- The Investigator will be responsible for the following:
 - Providing written summaries of the status of the study to the IRB/IEC annually or more frequently in accordance with the requirements, policies, and procedures established by the IRB/IEC.
 - Notifying the IRB/IEC of SAEs or other significant safety findings as required by IRB/IEC procedures.
 - Providing oversight of the conduct of the study at the site and adherence to requirements of 21 CFR, ICH guidelines, the IRB/IEC, European regulation 536/2014 for clinical studies (if applicable), and all other applicable local regulations.

10.1.2 Financial disclosure

Investigators and sub-Investigators will provide the Sponsor with sufficient, accurate financial information as requested to allow the Sponsor to submit complete and accurate financial certification or disclosure statements to the appropriate regulatory authorities. Investigators are responsible for providing information on financial interests during the course of the study and for 1 year after completion of the study.

10.1.3 Informed Consent Process

- The Investigator or his/her representative will explain the nature of the study to the participant or his/her legally authorized representative and answer all questions regarding the study.
- Participants must be informed that their participation is voluntary. Participants or their legally authorized representative (if acceptable by local regulations) will be required to sign a statement of informed consent that meets the requirements of 21 CFR 50, local regulations, ICH guidelines, Health Insurance Portability and Accountability Act requirements, where applicable, and the IRB/IEC or study center.
- The medical record must include a statement that written informed consent was obtained before the participant was enrolled in the study and the date the written consent was obtained. The authorized person obtaining the informed consent must also sign the ICF.
- Participants must be re-consented to the most current version of the ICF(s) during their participation in the study.
- A copy of the ICF(s) must be provided to the participant or the participant's legally authorized representative.

Participants who are rescreened are required to sign a new ICF.

The Investigator or authorized designee will explain to each participant the objectives of the exploratory research. Participants will be told that they are free to refuse to participate and may withdraw their consent at any time and for any reason during the storage period. A separate signature will be required to document a participant's agreement to allow any remaining specimens to be used for exploratory research. Participants who decline to participate in this optional research will not provide this separate signature.

10.1.4 Data Protection

All personal data collected related to participants, Investigators, or any person involved in the study, which may be included in the Sponsor's databases, shall be treated in compliance with all applicable laws and regulations including the Global Data Protection Regulation.

Data collected must be adequate, relevant and not excessive, in relation to the purposes for which they are collected. Each category of data must be properly justified and in line with the study objective.

Subject race and ethnicity will be collected in this study because these data are required by several regulatory agencies (eg, on afro American population for the FDA or on Japanese population for the Pharmaceuticals and Medical Devices Agency in Japan).

- Participants will be assigned a unique identifier by the Sponsor. Any participant records or datasets that are transferred to the Sponsor will contain the identifier only; participant names or any information which would make the participant identifiable will not be transferred.

- The participant must be informed that his/her personal study-related data will be used by the Sponsor in accordance with local data protection law. The level of disclosure must also be explained to the participant.
- The participant must be informed that his/her medical records may be examined by Clinical Quality Assurance auditors or other authorized personnel appointed by the Sponsor, by appropriate IRB/IEC members, and by inspectors from regulatory authorities.
- When archiving or processing personal data pertaining to the Investigator and/or to the participants, the Sponsor shall take all appropriate measures to safeguard and prevent access to this data by any unauthorized third party.

10.1.5 Committees Structure

Not applicable.

10.1.6 Dissemination of Clinical Study Data

Sanofi shares information about clinical trials and results on publicly accessible websites, based on company commitments, international and local legal and regulatory requirements, and other clinical trial disclosure commitments established by pharmaceutical industry associations. These websites include clinicaltrials.gov, [EU clinicaltrialregister \(eu.ctr\)](http://EU-clinical-trial-register.europa.eu), and sanofi.com, as well as some national registries.

In addition, results from clinical trials in patients are required to be submitted to peer-reviewed journals following internal company review for accuracy, fair balance and intellectual property. For those journals that request sharing of the analyzable data sets that are reported in the publication, interested researchers are directed to submit their request to clinicalstudydatarequest.com.

Individual participant data and supporting clinical documents are available for request at clinicalstudydatarequest.com. While making information available we continue to protect the privacy of participants in our clinical trials. Details on data sharing criteria and process for requesting access can be found at this web address: clinicalstudydatarequest.com.

10.1.7 Data Quality Assurance

- All participant data relating to the study will be recorded on printed or electronic CRF unless transmitted to the Sponsor or designee electronically (eg, laboratory data). The Investigator is responsible for verifying that data entries are accurate and correct by physically or electronically signing the CRF.
- The Investigator must maintain accurate documentation (source data) that supports the information entered in the CRF.
- The Investigator must permit study-related monitoring, audits, IRB/IEC review, and regulatory agency inspections and provide direct access to source data documents.

- The Sponsor or designee is responsible for the data management of this study including quality checking of the data.
- Study monitors will perform ongoing source data verification to confirm that data entered into the CRF by authorized site personnel are accurate, complete, and verifiable from source documents; that the safety and rights of participants are being protected; and that the study is being conducted in accordance with the currently approved protocol and any other study agreements, ICH GCP, and all applicable regulatory requirements.
- Records and documents, including signed ICFs, pertaining to the conduct of this study must be retained by the Investigator for 25 years after the end of the clinical study unless local regulations or institutional policies require a longer retention period. No records may be destroyed during the retention period without the written approval of the Sponsor. No records may be transferred to another location or party without written notification to the Sponsor.

10.1.8 Source documents

- Source documents provide evidence for the existence of the participant and substantiate the integrity of the data collected. Source documents are filed at the Investigator's site.
- Data reported on the CRF or entered in the eCRF that are transcribed from source documents must be consistent with the source documents or the discrepancies must be explained. The Investigator may need to request previous medical records or transfer records, depending on the study. Also, current medical records must be available.
- Definition of what constitutes source data can be found in Study Reference Manual.

10.1.9 Study and Site Closure

The Sponsor or designee reserves the right to close the study site or terminate the study at any time for any reason at the sole discretion of the Sponsor. Study sites will be closed upon study completion. A study site is considered closed when all required documents and study supplies have been collected and a study site closure visit has been performed.

The Investigator may initiate study site closure at any time, provided there is reasonable cause and sufficient notice is given in advance of the intended termination.

Reasons for the early closure of a study site by the Sponsor or Investigator may include but are not limited to:

- Failure of the Investigator to comply with the protocol, the requirements of the IRB/IEC or local health authorities, the Sponsor's procedures, or GCP guidelines.
- Inadequate recruitment of participants by the Investigator.
- Discontinuation of further study intervention development.

10.1.10 Publication Policy

- The results of this study may be published or presented at scientific meetings. If this is foreseen, the Investigator agrees to submit all manuscripts or abstracts to the Sponsor before submission. This allows the Sponsor to protect proprietary information and to provide comments.
- The Sponsor will comply with the requirements for publication of study results. In accordance with standard editorial and ethical practice, the Sponsor will generally support publication of multicenter studies only in their entirety and not as individual site data. In this case, a coordinating Investigator will be designated by mutual agreement.
- Authorship will be determined by mutual agreement and in line with International Committee of Medical Journal Editors authorship requirements.

10.2 APPENDIX 2: CLINICAL LABORATORY TESTS

- Urine human chorionic gonadotropin pregnancy test (as needed for women of childbearing potential) will be performed by the local laboratory.
- The local laboratory results used to make a study intervention decision or response evaluation must be entered into the CRF.
- Protocol-specific requirements for inclusion or exclusion of participants are detailed in [Section 5](#) of the protocol.
- Additional tests may be performed at any time during the study as determined necessary by the Investigator or required by local regulations.

Investigators must document their review of each laboratory safety report.

Laboratory/analyte results that could unblind the study will not be reported to investigative sites or other blinded personnel until the study has been unblinded.

10.3 APPENDIX 3: ADVERSE EVENTS: DEFINITIONS AND PROCEDURES FOR RECORDING, EVALUATING, FOLLOW-UP, AND REPORTING

DEFINITION OF AE

AE definition

- An AE is any untoward medical occurrence in a patient or clinical study participant, temporally associated with the use of study intervention, whether or not considered related to the study intervention.
- Note: An AE can therefore be any unfavorable and unintended sign (including an abnormal laboratory finding), symptom, or disease (new or exacerbated) temporally associated with the use of study intervention.

Events meeting the AE definition

- Any abnormal laboratory test results (hematology, clinical chemistry, or urinalysis) or other safety assessments (eg, electrocardiogram [ECG], radiological scans, vital signs measurements), including those that worsen from baseline, considered clinically significant in the medical and scientific judgment of the Investigator (ie, not related to progression of underlying disease).
- Exacerbation of a chronic or intermittent pre-existing condition including either an increase in frequency and/or intensity of the condition.
- New conditions detected or diagnosed after study intervention administration even though it may have been present before the start of the study.
- Signs, symptoms, or the clinical sequelae of a suspected drug-drug interaction.
- Signs, symptoms, or the clinical sequelae of a suspected overdose of either study intervention or a concomitant medication.
- "Lack of efficacy" or "failure of expected pharmacological action" per se will not be reported as an AE or SAE. Such instances will be captured in the efficacy assessments. However, the signs, symptoms, and/or clinical sequelae resulting from lack of efficacy will be reported as AE or SAE if they fulfil the definition of an AE or SAE.
- The signs, symptoms, and/or clinical sequelae resulting from lack of efficacy will be reported as AE or SAE if they fulfil the definition of an AE or SAE. Also, "lack of efficacy" or "failure of expected pharmacological action" also constitutes an AE or SAE.

Events **NOT** meeting the AE definition

- Any clinically significant abnormal laboratory findings or other abnormal safety assessments which are associated with the underlying disease, unless judged by the Investigator to be more severe than expected for the participant's condition.
- The disease/disorder being studied or expected progression, signs, or symptoms of the disease/disorder being studied, unless more severe than expected for the participant's condition.
- Medical or surgical procedure (eg, endoscopy, appendectomy): the condition that leads to the procedure is the AE.
- Situations in which an untoward medical occurrence did not occur (social and/or convenience admission to a hospital).
- Anticipated day-to-day fluctuations of pre-existing disease(s) or condition(s) present or detected at the start of the study that do not worsen.

DEFINITION OF SAE

If an event is not an AE per definition above, then it cannot be an SAE even if serious conditions are met (eg, hospitalization for signs/symptoms of the disease under study, death due to progression of disease).

A SAE is defined as any untoward medical occurrence that, at any dose:

A) Results in death

a) Is life-threatening

The term “life-threatening” in the definition of “serious” refers to an event in which the participant was at risk of death at the time of the event. It does not refer to an event, which hypothetically might have caused death, if it were more severe.

b) Requires inpatient hospitalization or prolongation of existing hospitalization

In general, hospitalization signifies that the participant has been detained (usually involving at least an overnight stay) at the hospital or emergency ward for observation and/or treatment that would not have been appropriate in the physician’s office or outpatient setting. Complications that occur during hospitalization are AEs. If a complication prolongs hospitalization or fulfills any other serious criteria, the event is serious. When in doubt as to whether “hospitalization” occurred or was necessary, the AE should be considered serious.

Hospitalization for elective treatment of a pre-existing condition that did not worsen from baseline is not considered an AE.

c) Results in persistent disability/incapacity

- The term disability means a substantial disruption of a person’s ability to conduct normal life functions.
- This definition is not intended to include experiences of relatively minor medical significance such as uncomplicated headache, nausea, vomiting, diarrhea, influenza, and accidental trauma (eg, sprained ankle) which may interfere with or prevent everyday life functions but do not constitute a substantial disruption.

d) Is a congenital anomaly/birth defect

e) Other situations:

- Medical or scientific judgment should be exercised in deciding whether SAE reporting is appropriate in other situations such as important medical events that may not be immediately life-threatening or result in death or hospitalization but may jeopardize the participant or may require medical or surgical intervention to prevent 1 of the other outcomes listed in the above definition. These events should usually be considered serious.

Examples of such events include invasive or malignant cancers, intensive treatment in an emergency room or at home for allergic bronchospasm, blood dyscrasias or convulsions that do not result in hospitalization, or development of drug dependency or drug abuse.

RECORDING AND FOLLOW-UP OF AE AND/OR SAE

AE and SAE recording

- When an AE/SAE occurs, it is the responsibility of the Investigator to review all documentation (eg, hospital progress notes, laboratory reports, and diagnostics reports) related to the event.
- The Investigator will then record all relevant AE/SAE information in the CRF.
- It is **not** acceptable for the Investigator to send photocopies of the participant's medical records to Sponsor in lieu of completion of the AE/SAE CRF page.
- There may be instances when copies of medical records for certain cases are requested by Sponsor. In this case, all participant identifiers, with the exception of the participant number, will be redacted on the copies of the medical records before submission to Sponsor.
- The Investigator will attempt to establish a diagnosis of the event based on signs, symptoms, and/or other clinical information. Whenever possible, the diagnosis (not the individual signs/symptoms) will be documented as the AE/SAE.

Assessment of intensity

The Investigator will make an assessment of intensity for each AE and SAE reported during the study and assign it to 1 of the following categories:

- **Mild:** An event that is easily tolerated by the participant, causing minimal discomfort and not interfering with everyday activities.
- **Moderate:** An event that causes sufficient discomfort and interferes with normal everyday activities.
- **Severe:** An event that prevents normal everyday activities. An AE that is assessed as severe should not be confused with a SAE. Severe is a category utilized for rating the intensity of an event; and both AEs and SAEs can be assessed as severe.

An event is defined as "serious" when it meets at least 1 of the predefined outcomes as described in the definition of an SAE, NOT when it is rated as severe.

Assessment of causality

- The Investigator is obligated to assess the relationship between study intervention and each occurrence of each AE/SAE.
- A "reasonable possibility" of a relationship conveys that there are facts, evidence, and/or arguments to suggest a causal relationship, rather than a relationship cannot be ruled out.
- The Investigator will use clinical judgment to determine the relationship.

- Alternative causes, such as underlying disease(s), concomitant therapy, and other risk factors, as well as the temporal relationship of the event to study intervention administration will be considered and investigated.
- The Investigator will also consult the IB and/or Product Information, for marketed products, in his/her assessment.
- For each AE/SAE, the Investigator **must** document in the medical notes that he/she has reviewed the AE/SAE and has provided an assessment of causality.
- There may be situations in which an SAE has occurred, and the Investigator has minimal information to include in the initial report to Sponsor. However, **it is very important that the Investigator always make an assessment of causality for every event before the initial transmission of the SAE data to Sponsor.**
- The Investigator may change his/her opinion of causality in light of follow-up information and send a SAE follow-up report with the updated causality assessment.
- The causality assessment is 1 of the criteria used when determining regulatory reporting requirements.

Follow-up of AEs and SAEs

- The Investigator is obligated to perform or arrange for the conduct of supplemental measurements and/or evaluations as medically indicated or as requested by Sponsor to elucidate the nature and/or causality of the AE or SAE as fully as possible. This may include additional laboratory tests or investigations, histopathological examinations, or consultation with other health care professionals.
- If a participant dies during participation in the study or during a recognized follow-up period, the Investigator will provide Sponsor with a copy of any post-mortem findings including histopathology.
- New or updated information will be recorded in the originally completed CRF.
- The Investigator will submit any updated SAE data to the Sponsor within 24 hours of receipt of the information.

REPORTING OF SAES

SAE reporting to Sponsor via an electronic data collection tool

- The primary mechanism for reporting an SAE to Sponsor will be the electronic data collection tool.
- If the electronic system is unavailable for more than 24 hours, then the site will use the paper SAE data collection tool (see next section).
- The site will enter the SAE data into the electronic system as soon as it becomes available.
- After the study is completed at a given site, the electronic data collection tool will be taken off-line to prevent the entry of new data or changes to existing data.

- If a site receives a report of a new SAE from a study participant or receives updated data on a previously reported SAE after the electronic data collection tool has been taken off-line, then the site can report this information on a paper SAE form (see next section) or to the [medical monitor/SAE coordinator] by telephone.
- Contacts for SAE reporting can be found in Study Reference Manual.

SAE reporting to Sponsor via paper CRF

- Facsimile transmission of the SAE paper CRF is the preferred method to report the SAEs when the electronic system is unavailable for more than 24 hours or when the electronic system has been taken off-line. The guidelines for reporting SAEs via paper CRF will be provided in the Study Reference Manual.
- In rare circumstances and in the absence of facsimile equipment, notification by telephone is acceptable with a copy of the SAE data collection tool sent by overnight mail or courier service.
- Initial notification via telephone does not replace the need for the Investigator to complete and sign the SAE CRF pages within the designated reporting time frames.
- Contacts for SAE reporting can be found in Study Reference Manual.

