 - Change from baseline to week 12 in Dermatology Life Quality Index (DLQI) total score.
 - Change from baseline to week 12 in PROMIS Sleep Related Impairment SF8a Total Score.
 - To continue to assess the safety and tolerability of dupilumab throughout the study.
 - Incidence of adverse events through week 12.
 - Incidence of adverse events through week 24.
-

Overall design:

This is a Phase IV, prospective, randomized, multinational study, with a 12-week double-blind placebo-controlled period, followed by a 12-week open label extension to evaluate the effect of dupilumab on sleep in adult patients with moderate to severe AD.

Number of participants:

Approximately 201 participants will be randomly assigned to study intervention in a 2:1 dupilumab to placebo ratio from multiple sites globally such that at least 150 evaluable participants (100 in the active group and 50 in placebo) complete the double-blind portion (to week 12) of the study.

Intervention groups and duration:

The study will comprise of:

- Screening period 1 (Day -28 to Day -8).
- Screening period 2 (Pre-baseline assessments): patients eligible to continue, will complete assessments specified in schedule of activities (SoA) from Day -7 to Day -1 (right before Day 1). If preferred by the patient and the investigator for logistical reasons, screening can be done during a single on-site visit. In that case, all procedures planned at screening 1 and screening 2 should be done during this single screening visit. Importantly, this single screening visit will have to be done at least 7 days before the baseline visit, as patients should wear the actigraph and complete the diary for 7 days before baseline.
- Baseline/Randomization/Administration of first dose (Day 1).
- 12-week double-blind placebo-controlled period: patients will be randomized to receive dupilumab or placebo.

- 12-week open-label extension period: following completion of double-blind period, patients randomized to dupilumab will continue to receive active treatment in the open-label period, whereas patients randomized to placebo will receive active treatment with dupilumab.

The maximum study duration per participant will be up to 28 weeks.

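### Protocol 10.3 gives opposite rules on whether lack of efficacy is an adverse event, so AE and SAE incidence can vary by site and take in efficacy failure

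*Protocol*

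**What the plan says.** Protocol 10.3 (Appendix 3) has a list headed "Events meeting the AE definition". Two adjacent bullets in it deal with lack of efficacy, or failure of the expected pharmacological action.

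- The first says that this "per se will not be reported as an AE or SAE" and adds: "Such instances will be captured in the efficacy assessments".
- The second ends by saying that it "also constitutes an AE or SAE".

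The two bullets agree on one thing: signs, symptoms and "clinical sequelae resulting from lack of efficacy will be reported as AE or SAE if they fulfil the definition".

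The companion list of events that do not meet the AE definition excludes "expected progression, signs, or symptoms of the disease/disorder being studied", unless they are more severe than expected for that patient. It does not mention lack of efficacy.

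"Incidence of adverse events through week 12", and the same measure through Week 24, are secondary endpoints (Protocol 1.1 and Section 3, Table 1). SAP 9.1 and 9.1.1 count treatment-emergent events as reported, with no rule that removes or separates lack-of-efficacy records. SAP 9 presents safety by actual treatment group, for the double-blind period and for the overall period. SAP 4.3.6 labels a patient who receives both placebo and dupilumab as dupilumab in as-treated analyses.

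**The concern.** A site cannot follow both bullets. One site may record a treatment failure as an adverse event while another leaves the same failure to the efficacy scales, and each can point to the protocol. The SAP then pools the two practices.

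The conflict also touches SAE reporting. Protocol 10.3 says that an event outside the AE definition cannot be an SAE, and Protocol 8.3.1 requires SAEs to be reported within 24 hours. Sites thus have opposite instructions on a reporting duty.

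In a placebo-controlled trial the added events need not fall evenly. The trial's hypothesis is that dupilumab is superior (Protocol 9.1). If so, lack of efficacy should be more frequent on placebo up to Week 12, and recording it as an adverse event would put part of the efficacy difference into the safety comparison.

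**Working it through.** **The text.** The conflict is in the current protocol body. Neither amendment summary corrects it, and no other section of the protocol or SAP says which bullet governs. It looks like two template alternatives left side by side: the appendices hold other unfinished template text, such as the unfilled time placeholder in note b to Table 6 (Protocol 10.4).

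**Inputs.** The documents give no AE rate and no lack-of-efficacy rate, so there is no stated figure to reproduce. From the documents: about 201 patients randomised 2:1, that is 134 dupilumab and 67 placebo. Assumed: background AE incidence b = 50% in both arms, and lack of efficacy f recorded for 20% of placebo and 8% of dupilumab patients, with two other pairs for range.

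**Effect on incidence if every site follows the second bullet.** Incidence counts patients, so a lack-of-efficacy record matters only for a patient with no other adverse event. With the same kind of overlap in both arms:

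- full overlap (f no larger than b): incidence = b
- independence: incidence = b + (1 − b) × f
- no overlap: incidence = b + f

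For 20% v 8%:

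- full overlap: 50% v 50%, difference 0 points
- independence: 0.50 + 0.50 × 0.20 = 60% v 0.50 + 0.50 × 0.08 = 54%, difference 6 points
- no overlap: 70% v 58%, difference 12 points

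| Lack of efficacy, placebo v dupilumab | Full overlap | Independence | No overlap |
|---|---|---|---|
| 10% v 5% | 0 | 2.5 | 5 |
| 20% v 8% | 0 | 6 | 12 |
| 30% v 10% | 0 | 10 | 20 |

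**Effect if only some sites follow it.** With a share s of patients at such sites, and independence, incidence = b + (1 − b) × s × f. For s = 0 the difference is 0. For s = 0.5 and 20% v 8% it is 55% v 52%, or 3 points. A wider grid (b of 30% or 60%; f of 30/10, 40/30, 50/25 or 70/40%) gives 2.0 to 10.5 points at s = 0.5 and 4.0 to 21.0 points at s = 1, all higher on placebo.

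**By count.** Placebo holds most of the records only if 67 × f(placebo) > 134 × f(dupilumab), that is, if its risk is more than twice that on dupilumab. At 20% v 8% the records are 13.4 v 10.7, so placebo holds 13.4 / 24.1 = 56%. At 10% v 5% they are 6.7 v 6.7, an even split.

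**The as-treated label.** Placebo patients receive dupilumab from Week 12. Suppose 80% of them enter the open-label period (assumed), with the same 20% risk in those who do and do not. Under SAP 4.3.6, 0.8 × 13.4 = 10.7 placebo-period records then move to the dupilumab column. That column holds 21.4 records among 134 + 53.6 = 187.6 patients (11.4%), and placebo keeps 2.7 among 13.4 (20%). If all enter, dupilumab holds 24.1 of 201 (12.0%) and the placebo column is empty. The balance of records reverses; whether the rates do depends on who fails to enter. Read literally, the label applies to double-blind as-treated tables too.

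**The case against.** The strongest reply is that little turns on this. AE results are numbers and percentages (Protocol 9.4.2), no between-arm AE test is planned, AE incidence is outside the testing hierarchy (SAP 8.2.23), and no efficacy conclusion depends on it. This stands, and it limits the consequence. It does not tell a site which bullet to follow.

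A second reply is overlap. Both bullets already make the signs, symptoms and sequelae of lack of efficacy reportable when they meet the AE definition, and exacerbation of a pre-existing condition is listed as an adverse event. Many patients with a recorded treatment failure may be counted anyway. This stands: the dispute covers only lack of efficacy as such, and the shift could be nil.

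Three stronger readings are tempting, and the documents do not support them.

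- A reader might infer that treatment failure is counted mainly against placebo, so that dupilumab looks safer than it is. No rates are given, 2:1 allocation means that it need not hold by count, and SAP 4.3.6 can move placebo-period events to dupilumab.
- A reader might infer that the list of events not meeting the definition settles the matter for the first bullet. It concerns expected signs and symptoms of the disease and is only a neighbouring rule.
- A reader might infer that the analysis cannot repair this. The SAP as written does not, but events are coded and tabulated by preferred term, so records of lack of efficacy alone should be identifiable.

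**Conclusion.** The point holds as an internal contradiction that needs correcting. Protocol 10.3 gives opposite instructions on lack of efficacy as such, nothing resolves them, and the SAP has no filter. AE and SAE incidence can therefore depend on site practice and can include efficacy failure.

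In the double-blind period the excess is probably at a higher rate on placebo. That rests on dupilumab working and on at least some sites following the second bullet. The size cannot be fixed from the documents: 0, 6 or 12 points in the main illustration, according to overlap, with all inputs assumed and overlap taken to be alike in both arms. These figures show what could happen; they do not estimate a bias. In as-treated whole-study tables the direction could reverse.

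**What to change.** Reconcile the two bullets into one rule, with the sponsor confirming which is intended. If the first bullet stands, remove the whole second bullet, since without its last sentence it only repeats the first, and move the rule to the list of events that do not meet the AE definition. Deleting the last sentence alone would leave a duplicate, and a not-reported rule under a heading for events that are reported. Remind sites of the confirmed rule.

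Before database lock, while SAP Section 1 still allows changes, add one double-blind TEAE table by randomised arm that leaves out events recorded only as lack of efficacy. Using the randomised arm avoids the relabelling in SAP 4.3.6.

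The cost is a small protocol amendment, which needs IRB/IEC approval before implementation (Protocol 10.1.1), a site reminder and one extra table. If the first rule is confirmed, little information is lost, since the efficacy endpoints already measure treatment failure.
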